5.4.2 Target Lesion Pre-Treatment

The target lesion(s) must be pre-dilated with standard percutaneous transluminal balloon angioplasty. *In accordance with the Instructions for Use, this trial does not allow for direct stenting of the target vessel(s).*

Attention must be paid to the pre-dilatation technique in order to avoid balloon injury to any segment of the vessel that will not be entirely covered by the stent (“geographical miss”).

Pre-dilatation must be performed using a balloon with the following three characteristics:

1. For lesions treated with a 2.0 mm stent, the pre-dilation balloon used must be ≤ 1.75 mm in diameter.
2. A length matching or shorter than the lesion length to be dilated (to avoid dilatation of the vessel wall adjacent to the stent)
3. A length shorter than the stent to be implanted

The use of other therapy (e.g., cutting balloons, atherectomy, laser, thrombectomy, etc.) is not allowed.

5.4.3 Enrollment

All subjects who meet general eligibility requirements will be asked to participate. Subjects will be considered enrolled into the trial after the following criteria have been met:

1. The signed informed consent has been obtained
2. The study stent (Resolute Onyx 2.0 mm stent) is introduced into the guide catheter

In cases where the procedure is stopped prior to the study stent being delivered into the guide catheter (e.g., subject becomes unstable, power outage, equipment issues, etc.), the subject will not be considered enrolled and will be replaced.

Subject enrollment and stent use information will be submitted to the sponsor on the eCRF within 1 working day or as soon as source documents are available.

5.4.4 Stenting Procedure

The aim is to maintain a homogeneous treatment strategy, and therefore all lesions should be treated with Resolute Integrity (2.25 mm - 4.0 mm) or Resolute Onyx (2.0 mm) stents. Potential interaction with other drug-eluting stents or coated stents has not been evaluated, and should be avoided.

RESOLUTE Onyx 2.0 mm Clinical Study
CONFIDENTIAL - May not be reproduced without written permission from Medtronic

A stent length should be selected so that the lesion can be covered with a single stent in order to avoid the use of multiple stents. Careful stent sizing is important to successful stenting. In general, the stent size should be chosen to match the diameter of the reference vessel and to correspond with the length of the lesion. The appropriate Resolute Onyx Stent size selected for the target lesion must be ≥ 3 mm longer than the lesion length in order to provide 1.5 mm of stent coverage on either side of the lesion.

The stent system will be prepared according to the Resolute Onyx Stent System IFU. The prepared delivery system will be advanced over the guide wire, through the guiding catheter to the target lesion site. The stent will be positioned across the lesion and placement will be confirmed by fluoroscopic angiographic test injections. Deployment of the stent should then be performed in accordance with the IFU.

Available Resolute Onyx 2.0 mm stent sizes are listed in [Table 5](#).

Table 5: Resolute Onyx 2.0 mm Stent Size Matrix

Nominal Expanded Inner Diameter (mm)	Stent Length (mm)						
	8	12	15	18	22	26	30
2.0	✓	✓	✓	✓	✓	✓	✓

Post-dilatation may be performed at the Investigator's discretion with appropriately sized (length and diameter) non-compliant balloon to assure that the stent is in full contact with the vessel wall. ***Do not use the stent delivery balloon for post-dilatation.***

For subjects with planned treatment of two lesions, ***the first lesion must be treated successfully and the subject must be clinically stable before treatment of the second lesion is attempted.***

Successful treatment of the first lesion is defined as:

- <10% residual diameter stenosis result is achieved (visual assessment)
- TIMI 3 flow is present post treatment
- No evidence of dissection (NHLBI Type C, D, E or F), thrombus or distal embolization at the first study lesion site post-treatment.

Prior to attempted treatment of the second study lesion, subjects must be clinically stable without angina or ECG changes consistent with coronary ischemia. If the subject is not clinically stable, or shows signs or symptoms of possible coronary ischemia following treatment of the first study lesion, treatment of the second lesion should be deferred, if possible. Subsequent treatment of the second lesion should be with a study stent if performed during the trial index procedure. If the second lesion requires treatment after the index procedure, a non-study stent must be used.

For subjects with planned treatment of only one lesion but during the procedure a second lesion meeting trial criteria is identified, a Resolute Integrity (2.25 mm - 4.0 mm) or Resolute Onyx (2.0 mm) stent should be used if stenting is needed and treatment cannot be deferred. If the lesion does not meet trial criteria, a non-study stent should be used if stenting is needed and the lesion will be considered a non-target lesion for purposes of analysis.

RESOLUTE Onyx 2.0 mm Clinical Study**CONFIDENTIAL - May not be reproduced without written permission from Medtronic**

5.4.5 Bailout

Bailout procedures should be avoided unless required for subject safety. If bailout procedures are performed, justification should be documented on the CRF.

If a subject in the trial experiences a major dissection or an occlusive complication (as evidenced by decreased target vessel flow, chest pain, or ischemic electrocardiogram (ECG) changes which do not respond to standard rescue techniques), bailout procedures may be performed. For these events occurring during the study procedure, additional stenting with Resolute Integrity (2.25 mm - 4.0 mm) or Resolute Onyx (2.0 mm) stents may be employed as a bailout treatment.

In this trial, the target lesion(s) is/are to be selected with the intent to cover each lesion with a single stent. If incomplete coverage occurs during the procedure, additional stenting with study stents may be employed to provide complete coverage.

It is recommended to overlap the Resolute Onyx stents 1-2 mm to avoid the potential for gap restenosis.

5.4.6 Treatment Failure

Following subject enrollment, study stent(s) that enter the guide catheter and fail to be implanted at the intended location are considered treatment failures and will be recorded in the eCRF. In the event of a failure to implant at least one study stent, the Investigator may choose to treat the target lesion(s) with any approved stent. Treatment failures will be followed-up for safety purposes through 12-months and will be included in the intent-to-treat (ITT) population. The subject will undergo the follow-up assessments listed in [Section 5.6](#) through the 12 month follow-up assessment.

Note: Damaged or failed Resolute Onyx Stent Systems (including ancillary devices) must be returned to the Medtronic Product Experience Management Department per instructions provided by Medtronic.

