4.4 Subject Selection

All subjects presenting to the cardiac catheterization laboratory for possible interventional treatment are potential candidates. Those subjects who sign the Institutional Review Board (IRB) approved informed consent and subsequently fulfill all inclusion criteria and no exclusion criteria will be enrolled in the trial.

RESOLUTE Onyx 2.0 mm Clinical Study**CONFIDENTIAL - May not be reproduced without written permission from Medtronic**

Screening of candidates for this trial should include assessment of the need for anticipated treatment of other target vessel lesions likely to be needed within 12 months post-procedure. Candidates in whom it is likely that other obstructive lesions will require treatment within the target vessel(s) within 12 months post-procedure should not be enrolled in this trial, as assessment of key safety endpoints will occur at 12 months post-procedure.

Per intent-to-treat principles (ITT), subjects who did not have a study stent (Resolute Onyx 2.0 mm stent) implanted but a study stent was introduced into the guide catheter will be followed through 12 months.

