5.6 Follow-Up Requirements

5.6.1 Follow-up General Requirements

The general requirements for follow-up in this trial include:

1. Enrolled subjects who received a study stent will be followed for 3 years after the index procedure by authorized study staff at the investigational site. See [Table 6](#) for follow-up assessment requirements.
2. Subjects in the 2.0 mm Angio subset will return to the site where the procedure was performed for a 13-month clinic visit including an angiogram. Other follow-up contacts will be conducted by telephone, e-mail or clinical visit, unless an unscheduled clinic visit occurs during a follow-up window.
3. A missed follow-up assessment will be documented by the investigator and reported in the eCRF, including the reason for the missed follow-up assessment in the subject's file.
4. Clinical assessments (e.g., angina status, use of antiplatelet medication, new and ongoing adverse events; medical, surgical or dental procedures and the interruption, if any, to antiplatelet therapy) must be performed at each follow-up contact and prior to any interventional procedure (e.g., angiography, PCI) during the 3-year follow-up period.
5. Documentation of referring physicians, general practitioners, cardiologists and family members should be noted to facilitate continued ability to contact a study subject. Any planned long absences by the subject from the area should also be noted.
6. Angiography should be performed for any post-procedure clinical event (e.g., MI) to determine if the event is attributable to the target vessel(s) or a non-target vessel.

The schedule and method for follow-up contacts and windows for each contact is tabled below.

Table 6: Follow-up Contact Requirements

Follow-up Interval	Window	Method*
30 days	± 5 days	Contact
6 months	±14 days	Contact/Clinic Visit**
12 months	± 30 days	Contact
12 month Clinical Follow up must occur at least 1 day prior to the 13 month Angiographic Follow up		
13 months (2.0 mm Angio subset)	± 14 days	Clinic Visit (with Angio)
2 Year	± 30 days	Contact
3 Year	± 30 days	Contact

*Subject contact includes phone call, email or clinic visit

**Clinic visit for subjects with baseline MPI performed, otherwise subject contact visit

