6.2.3 Percutaneous Coronary Diagnostic and Treatment Procedures

Other risks associated with using this device are those associated with percutaneous coronary diagnostic (including angiography and IVUS) and treatment procedures. These risks (in alphabetical order) may include but are not limited to the following:

- Abrupt vessel closure
- Access site pain, hematoma or hemorrhage
- Allergic reaction (to contrast, antiplatelet therapy, stent material, or drug and polymer coating)
- Aneurysm, pseudoaneurysm, or arteriovenous fistula (AVF)
- Arrhythmias, including ventricular fibrillation
- Balloon rupture
- Bleeding
- Cardiac tamponade
- Coronary artery occlusion, perforation, rupture, or dissection
- Coronary artery spasm
- Death
- Embolism (air, tissue, device, or thrombus)
- Emergency surgery: peripheral vascular or coronary bypass
- Failure to deliver the stent
- Hemorrhage requiring transfusion
- Hypotension / hypertension
- Incomplete stent apposition
- Infection or fever
- Myocardial infarction (MI)
- Pericarditis
- Peripheral ischemia / peripheral nerve injury
- Renal Failure
- Restenosis of the stented artery
- Shock / pulmonary edema
- Stable or Unstable angina
- Stent deformation, collapse, or fracture
- Stent migration or embolization
- Stent misplacement
- Stroke / transient ischemic attack
- Thrombosis (acute, sub-acute or late)

RESOLUTE Onyx 2.0 mm Clinical Study**CONFIDENTIAL - May not be reproduced without written permission from Medtronic**

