- Angiographic perforation:** perforation detected by the clinical site or the core laboratory at any point during the procedure.
- Clinical perforation:** perforation requiring additional treatment (including efforts to seal the perforation or pericardial drainage), or resulting in significant pericardial effusion, acute closure, myocardial infarction, or death.
- Pericardial hemorrhage/tamponade:** perforation resulting in cardiac tamponade.

PROCEDURE SUCCESS

Attainment of < 50 % residual stenosis of the target lesion and no in-hospital MACE.

RESTENOTIC LESION

Defined as a lesion in a vessel segment that has undergone prior percutaneous treatment with or without a stent placement.

REFERENCE VESSEL DIAMETER (RVD)

Defined as the average of normal segments within 10 mm proximal and distal to the target lesion from two orthogonal views using QCA.

SERIOUS ADVERSE EVENT

A serious adverse event (SAE) is defined as an adverse medical occurrence that:

- a) led to death
- OR
- b) led to a serious deterioration in the health of a subject that either resulted in
 - 1) a life-threatening illness or injury, or
 - 2) a permanent impairment of a body structure or a body function, or
 - 3) in-patient or prolonged hospitalization, or
 - 4) medical or surgical intervention to prevent life-threatening illness or injury or permanent impairment to body structure or a body function
- OR
- c) led to fetal distress, fetal death or a congenital abnormality or birth defect.

RESOLUTE Onyx 2.0 mm Clinical Study**CONFIDENTIAL - May not be reproduced without written permission from Medtronic**

STENT THROMBOSIS

All stent thrombosis data will be reported per the Academic Research Consortium (ARC) definitions.

Academic Research Consortium (ARC) Definition:

Stent thrombosis should be reported as a cumulative value over time and at the various individual time points as specified below. Time 0 is defined as the time point after the guiding catheter has been removed and the subject has left the catheterization lab.

Timing:

Acute stent thrombosis *	0 – 24 hours post stent implantation
Subacute stent thrombosis *	> 24 hours – 30 days post stent implantation
Late stent thrombosis	> 30 days – 1 year post stent implantation
Very late stent thrombosis	> 1 year post stent implantation

* Acute or subacute stent thrombosis can also be replaced by the term early stent thrombosis.

Three categories of evidence define stent thrombosis: *Definite, Probable, Possible*

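### The 12-month stop in Protocol 5.4.6 turns on implantation at the intended location, which conflicts with the 3-year rule in 5.6.1 for a subject left with a misplaced or unretrieved study stent

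*Protocol*

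**What the plan says.** Protocol 5.4.6 defines failure by stent and by place: "study stent(s) that enter the guide catheter and fail to be implanted at the intended location are considered treatment failures". It continues: "Treatment failures will be followed-up for safety purposes through 12-months and will be included in the intent-to-treat (ITT) population". Its closing sentence moves from the stent to the subject, who has the Section 5.6 assessments only "through the 12 month follow-up assessment".

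Protocol 5.6.1, item 1, sets the general rule: "Enrolled subjects who received a study stent will be followed for 3 years after the index procedure".

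Protocol 4.4 applies 12-month follow-up to a narrower group, namely "subjects who did not have a study stent (Resolute Onyx 2.0 mm stent) implanted but a study stent was introduced into the guide catheter". Protocol 4.0 and SAP 3.1 likewise tie it to a 2.0 mm stent that was attempted but not implanted.

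Protocol 6.2.3 lists stent misplacement among the risks, and also "Stent migration or embolization". Protocol 3.2 and SAP 3.2.2 assess cardiac death, TVMI, MACE, TLF, TVF and stent thrombosis annually through year 3. Appendix 2 defines "Very late stent thrombosis" as occurring more than 1 year after implantation.

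**The concern.** Not being implanted and not being implanted where intended are different conditions. A stent deployed in the wrong segment meets the second but not the first. So does one that embolises and stays in the body, if implanted is taken to mean left in place. Protocol 5.4.6 uses the second condition to fix the length of follow-up; the other sections use the first, or its counterpart, receipt of a study stent.

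The section also uses a label that belongs to a stent to set a schedule that belongs to a subject. Protocol 5.4.5 permits additional study stents, and Protocol 7.4 foresees two lesions in one subject each treated with a 2.0 mm stent. One subject can therefore have both a failed study stent and an implanted one.

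At stake is late safety information on people who carry the device. Protocol 6.2.1 relates zotarolimus exposure to total implanted stent length and does not mention placement, so a misplaced stent is still exposure. Two sites could also follow identical subjects for different lengths of time, each with a section of the protocol in support.

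**Working it through.** The plan states no figure on this point. The check sets the rules side by side, then works out what an early exit would remove.

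**Step 1. Rule by type of subject.**

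| Subject at end of procedure | 5.4.6, read literally | 4.0, 4.4, SAP 3.1 | 5.6.1 | Result |
|---|---|---|---|---|
| No study stent in the body | 12 months | 12 months | 3-year rule not triggered | Consistent |
| Study stent deployed at an unintended site | 12 months | 12-month rule does not apply | 3 years | Conflict |
| Study stent embolised, not retrieved | 12 months | Depends on whether it counts as implanted | 3 years, if it counts as received | Conflict, with undefined terms |
| One study stent failed, another implanted as intended | 12 months, or not covered | 12-month rule does not apply on the 4.4 wording | 3 years | Ambiguous |

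Neither document ranks these sections or defines implanted or received for a stent left elsewhere.

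**Step 2. Observation lost per affected subject.** The schedule falls from 36 to 12 months: 36 − 12 = 24 months, or 2 of 3 years, with both the 2-year and 3-year contacts.

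For the very late period, SAP Appendix II puts the 12-month visit at 360 ± 30 days, so the last contact falls between day 330 and day 390. Taking 1 year as 365 days, at most 390 − 365 = 25 days of the period are seen. To the nominal 36-month day of 1080 it lasts 1080 − 365 = 715 days, and 25/715 = 3.5%. A contact before day 365 sees none of it.

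**Step 3. Number affected.** The documents give no frequency. Purely as an assumption, 2% to 5% of 100 subjects gives 2 to 5 subjects and 2 × 2 = 4 to 5 × 2 = 10 subject-years, out of a nominal 100 × 3 = 300 (1.3% to 3.3%). That range covers all three problem rows; the two clear conflicts alone would be fewer.

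**Step 4. Effect on the late rates.** Under SAP 6.1, the denominator holds subjects with an event by the time point, or with follow-up past the lower edge of the window. For 24 months that edge is 720 − 30 = day 690. An event-free subject who exits by day 390 leaves the denominator; one with an earlier event stays in both numerator and denominator.

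Illustration with assumed counts: 100 subjects, 5 affected, 1 of these with an early event, 10 events among the other 95, and the 4 event-free affected subjects exit.

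- Observed rate: 11/96 = 11.5%.
- Full follow-up, no late event among the 4: 11/100 = 11.0%. Early exit overstates the rate.
- Full follow-up, one late event among the 4: 12/100 = 12.0%. Early exit understates it.

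The two agree when the expected late events k among the 4 satisfy (11 + k)/100 = 11/96, so k = 0.46, a risk of 0.46/4 = 11.5% each. The direction therefore depends on whether the exiting subjects' later risk is above or below the observed cumulative rate.

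**Step 5. Primary endpoint.** Both rules follow every enrolled subject through 12 months, so TLF at 12 months is the same under either.

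**The case against.** The strongest reply is that 5.4.6 does not stand alone. Protocol 5.6.1 gives 3 years to enrolled subjects who received a study stent, Protocol 4.0 and 4.4 and SAP 3.1 keep the 12-month rule for stents not implanted, and Protocol 1.6 expects three years of participation from each subject. A reader might infer from 5.4.6 that subjects with a misplaced stent definitely leave at 12 months. The documents do not support that: the same subjects fall under 5.6.1, so early exit is a risk created by an unresolved conflict. This stands, and it limits the point to reconciliation.

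Second, a reader might add, as equally certain, subjects in whom a first study stent fails and a second is implanted, or who have two 2.0 mm lesions and one failure. The second sentence of 5.4.6, on failing to implant at least one study stent, can be read as meaning that none was implanted, and the sentence setting the subject's schedule comes after it. SAP Section 4 also works at subject level when it removes from the per-protocol set those who received no study device. The phrase is not clear, and grammatically it governs the choice of replacement stent, but these cases are only ambiguous. The argument does not reach a stent left at an unintended site.

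Third, a reader might infer that the late rates are biased in the device's favour. Step 4 shows that the denominator rule can push them either way. Favourable bias requires the exiting subjects' later risk to exceed the observed rate. That is conceivable, especially for a rare event such as stent thrombosis, but nothing in the documents shows it.

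Finally, the risk list in 6.2.3 shows that misplacement and embolisation are foreseen, not how often they occur. The secondary endpoints are descriptive only.

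**Conclusion.** The conflict is real and narrow. For a subject who leaves the procedure with a study stent at an unintended site, 5.4.6 read literally says 12 months and 5.6.1 says 3 years, with no rule of precedence. Where one study stent fails and another is implanted there is some ambiguity, but no clear contradiction.

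If a site follows 5.4.6, each such subject loses 2 of 3 planned years, including nearly all of the very late stent thrombosis period. The primary endpoint is untouched. The number affected is unknown and probably very small; the 2 to 5 subjects used above are an assumption. The effect on the descriptive 2- and 3-year rates has no established direction.

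For a misplaced stent the conclusion rests only on the wording. For an embolised stent it also assumes that received, in 5.6.1, includes a stent that remains in the body. The passages should be reconciled before subjects reach their 12-month contact, because data missed after an exit may not be recoverable.

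**What to change.** Reconcile 5.4.6 with Protocol 4.0, 4.4 and 5.6.1 and SAP 3.1:

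- Record treatment failure per stent on the eCRF, and set follow-up length per subject.
- State that the 12-month stop applies only to subjects with no study stent implanted.
- State that anyone who leaves the procedure with a study stent in the body, at any site, stays on the 5.6.1 schedule, even if another study stent failed.
- Match the EDC visit schedule to this rule.

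The cost is about one sentence in 5.4.6, the EDC change, and two further annual contacts per affected subject, which Table 6 allows by phone or e-mail. At the assumed 2 to 5 subjects that is 4 to 10 contacts. The change concerns data collection only; it alters no treatment and leaves the primary analysis as planned.

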5.4.7 End of Procedure

Upon procedure completion, an intracoronary injection of nitroglycerin must be administered and final angiography of the vessel(s) performed in the same two near-orthogonal views that were taken at baseline, showing the target lesion(s) free of foreshortening or vessel overlap, using a 6 French or larger guiding catheter (see [Appendix 7](#)).

The end of the procedure is defined as the time the guide catheter is removed from the subject. If the subject is returned to the procedure room and a guiding catheter is reinserted and a dilatation is performed, this should be considered a repeat intervention.

All adverse events that occur during the procedure must be recorded on the eCRF, including but not limited to dissections, acute closures, etc.

RESOLUTE Onyx 2.0 mm Clinical Study
CONFIDENTIAL - May not be reproduced without written permission from Medtronic

